#### 5.6.1.1 Primary Analysis of the Primary Endpoint

There is no formal hypothesis test for the primary endpoint.

The endpoint will be presented in tabular format, displaying the number and percentage of subjects with adverse events. Events will also be summarized by type and severity. Results will be based on observed events without imputation.

#### 5.6.2 Secondary Endpoint 1 - SSQ

The secondary endpoint 1 is defined as the difference between preoperative and postoperative performance on the Speech Spatial & Qualities of Hearing Questionnaire (SSQ) – Parent version at 6 months post-surgery.

### 5.6.2.1 Primary Analysis of Secondary Endpoint 1

Secondary endpoint 1 will be assessed with the following hypothesis:

 $H_0$ :  $\Delta \leq 0$ 

 $H_a: \Delta > 0$ 

where  $\Delta$  represents difference between preoperative and postoperative performance on the Speech Spatial & Qualities of Hearing Questionnaire (SSQ) – Parent version at 6 months post-surgery, specifically  $\Delta = SSQ_{6\,Months} - SSQ_{preop}$ . This difference is parameterized so that a positive value is indicative of a clinical improvement in the questionnaire.

The hypothesis will be evaluated using a one-sample, one-sided 0.025 alpha level t-test for a mean against the null of zero. The objective will be met if the null hypothesis is successfully rejected.

The endpoint will be presented with descriptive statistics and the corresponding two-sided 95% confidence interval based on the t-distribution.

#### 5.6.2.2 Handling of Missing Data

Little missing data is expected for this endpoint. If there is missing endpoint data, a multiple imputation approach will be used based on a fully conditional specification. The imputation model will include the following covariates: age, sex, and baseline SSQ. An augmented likelihood approach will be used if need

St	atistical Analysis Plan	Pa	ge 9 of 13
Sponsor	Study		Version
Cochlear Americas	A pivotal, prospective, multi-center, open- label study evaluating the safety and effectiveness of the Cochlear ™ Osia ® 2 System in a pediatric population		1.0

to facilitate modeling. A total of 100 imputed data sets will be generated and results combined for inferential purposes.

#### 5.6.2.3 Sensitivity Analysis

In the event there is significant evidence of a departure from normality based on a Shapiro-Wilk test at the 0.05 alpha level, a one-sample Sign test (a non-parametric alternative) will be employed.

A tipping point analysis for missing data will be performed as a sensitivity analysis. This will impute values for the missing endpoint data, using all possible combinations of the "best" and "worst" observed results for the endpoint (i.e. all missing imputed as "worst", all missing imputed as "best", and all combinations between these extremes).

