#### 3.2.2.2 Data from Non-Published Studies

Cochlear sponsored a pediatric, newly implanted, prospective, ITA clinical trial (Cochlear CAM5706, ITA# 272423) at the Hospital for Sick Children in Toronto, Ontario, Canada. The aim of the study was to gather preliminary safety and effectiveness information on the feasibility of implanting children aged 5 years to 17 years with the Osia System. Fourteen subjects were implanted, 15 ears, aged 10 to 17 years of age with a mean age of 13.9 years who presented with either mixed or conductive hearing loss. The primary objective was to quantify the type and severity of adverse events that occurred in the study cohort. A total of 15 adverse events were recorded for the 14 subjects. All adverse events were reported as resolved by study closure. The study reported 1 serious adverse event related to a thick skin flap which prohibited the link to the external sound processor. A revision surgery to reduce the thickness of the skin flap resolved the SAE and the subject completed the study successfully. In addition to safety information, surgical questionnaires, daily use and patient reported outcomes using the SSQ-12 Parent were collected. Surgical data revealed a relatively standard procedure using a C shaped incision, general anesthesia and receipt of a 4mm Bl300 implant fixture. Results of the study emphasized the importance of measuring skin flap thickness prior to implantation as well as the effectiveness of skin flap reduction in children. Daily use of the sound processor

post-operatively at six months revealed average use time of 8.4 hours daily indicating a significant use time during waking hours. Self-reported outcomes using the SSQ-12 Parent revealed a mean improvement of 2.10 for total score in the aided condition. Lastly, preliminary effectiveness data measured by both PTA 4 and speech perception in quiet using PBK monosyllabic words revealed a mean improvement in audibility of 31.7dB and a 79.1% improvement in the unaided to aided conditions respectively at 6 months postoperatively.

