### 4 Sample Size Determination

Sample size for the study is not driven by power requirements for a formal statistical hypothesis test. The planned sample size of 50 subjects will provide data to characterize safety and effectiveness with a reasonable degree of statistical precision. Additionally, the planned sample size will allow for a high probability of observing events of interest. For example, with 50 subjects, the half-width of a two-sided 95% confidence interval for a continuous endpoint based on a t-distribution would be 0.284 units on the effect size scale. Similarly, with 50 subjects, there is a greater than 95% probability of observing one or more events that occur at a population rate of 5.9%

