#### 5.6.4 Secondary Endpoint 3 – CNC Words

Secondary endpoint 3 is defined as the mean difference between baseline unaided speech perception in quiet and the aided condition using the Osia 2 system at 6 months post-surgery on open-set monosyllabic word recognition (CNC Words) in quiet.

### 5.6.4.1 Primary Analysis of Secondary Endpoint 3

The secondary endpoint 3 will be assessed with the following hypothesis:

 $H_0$ :  $\Delta \leq 0$ 

 $H_a$ :  $\Delta > 0$ 

where  $\Delta$  represents difference between baseline unaided speech perception CNC and 6 months-post surgery CNC, specifically  $\Delta$  =  $CNC_{6\,Months}$  –  $CNC_{preop}$ . This difference is parameterized so that a positive value is indicative of a clinical improvement.

The hypothesis will be evaluated using a one-sample, one-sided 0.025 alpha level t-test for a mean against the null of zero. The objective will be met if the null hypothesis is successfully rejected.

The endpoint will be presented with descriptive statistics and the corresponding two-sided 95% confidence interval based on the t-distribution.

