#### 5.6.4.3 Sensitivity Analysis

In the event there is significant evidence of a departure from normality based on a Shapiro-Wilk test at the 0.05 alpha level, a Sign test (a non-parametric alternative) will be employed.

A tipping point analysis for missing data will be performed as a sensitivity analysis. This will impute values for the missing endpoint data, using all possible combinations of the "best" and "worst" observed results for the endpoint (i.e. all missing imputed as "worst", all missing imputed as "best", and all combinations between these extremes).

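### The planned tipping point analysis is a best/worst-case enumeration: it can say how many missing children must be worst to lose significance, but not how large a departure from the imputation model is needed

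*SAP*

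**What the plan says.** SAP 5.6.2.3 states: "A tipping point analysis for missing data will be performed as a sensitivity analysis". The scenarios, given in the same terms for all four secondary endpoints (5.6.2.3, 5.6.3.3, 5.6.4.3, 5.6.5.3), are "all missing imputed as 'worst', all missing imputed as 'best', and all combinations between these extremes", where best and worst are observed results for that endpoint.

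Each endpoint is a within-child difference. For CNC it is the "mean difference between baseline unaided speech perception in quiet and the aided condition using the Osia 2 system at 6 months post-surgery", tested with a "one-sample, one-sided 0.025 alpha level t-test for a mean against the null of zero". The main handling of missing data is multiple imputation by fully conditional specification, with age, sex and the baseline value as covariates and 100 imputed sets (for CNC, SAP 5.6.4.2). The SAP expects little missing data and gives no rate. Protocol 6.2.6 does not replace participating subjects who withdraw.

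The only word-score effect in the documents is "a 79.1% improvement in the unaided to aided conditions" (Protocol 3.2.2.2). The same feasibility study reports a mean SSQ gain of 2.10. Neither figure comes with an SD.

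**The concern.** Best/worst filling suits a yes/no outcome, where two values exhaust the possibilities. For a continuous change it leaves three gaps.

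- The output is a count of children at the worst value. It does not say how much worse than the imputation model predicts the missing children would have to be.
- No scenario gives the missing children zero change from baseline, which is the natural reference for children who gained nothing.
- The worst value comes from children who were tested. If every tested child improves, the worst case still credits untested children with a gain.

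This is the only planned departure from the missing-at-random imputation model; the sign test in the same sections addresses non-normality. The four tests are run in sequence to support labelling claims (SAP 5.6), so how robust they are said to be matters.

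**Working it through.** **The plan's own figures.** The SAP gives no figure for this analysis. Its sample-size figures reproduce. With 50 subjects the half-width "would be 0.284 units on the effect size scale": t(0.975, 49)/√50 = 2.010/7.071 = 0.284. At an event rate of 5.9%, 1 - 0.941^50 = 0.952, which is above 95%.

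**Inputs.** n = 50 (SAP 4). Six missing is an assumption: the published adult study in Protocol 3.2.2.1 implanted 51 and reports 12-month outcomes in 45, so 6/51 = 11.8%, close to 6/50 = 12%. All SDs are assumptions. The 79.1% is read as percentage points. Observed changes are set to 44 normal scores scaled to the stated mean m and SD s.

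**Formulas.** If all six missing children receive one value v:

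- mean M = (44m + 6v)/50
- SD² = [43s² + (44 × 6/50)(m - v)²]/49
- t = M/(SD/√50), significant above 2.010

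For mixtures, the same t-test is applied to the 44 observed and 6 filled values. These are single fills, used for illustration in place of the full multiple imputation.

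**CNC at mean 79.1.** The expected minimum of 44 standard normal values is -2.199.

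- SD 20: expected worst 79.1 - 2.199 × 20 = +35. It is above zero in 99.8% of simulated samples.
- SD 30: expected worst 79.1 - 2.199 × 30 = +13. It is above zero in 83%.

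Zero change at SD 20: M = 3480.4/50 = 69.6; SD² = (43 × 400 + 5.28 × 79.1²)/49 = 1025; t = 69.6/(32.0/7.071) = 15.4. The all-worst fill gives t = 21.9. So the scenario called worst is milder than no benefit. With all six at -100, the scale limit, t is still 6.6.

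**SSQ, assumed mean 0.8 and SD 2.0.** Worst is -3.68 and best is +5.28.

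| Children at worst (of 6) | Average fill | One-sided p |
|---|---|---|
| 0 | +5.3 | 0.0001 |
| 1 | +3.8 | 0.0007 |
| 2 | +2.3 | 0.003 |
| 3 | +0.8 | 0.012 |
| 4 | -0.7 | 0.039 |
| 5 | -2.2 | 0.101 |
| 6 | -3.7 | 0.220 |

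Significance is lost at 4 of 6. Compare a common fill with the same average, -0.69. Both give M = 0.62. The mixture has SD 2.44 and t = 1.80. The common fill has SD² = (43 × 4 + 5.28 × 1.49²)/49 = 3.75, so SD 1.94 and t = 0.62/(1.94/7.071) = 2.26, which is significant. The flip comes from variance that mixing the two extremes adds. A common fill loses significance only at about -1.2, which is 2.0 points below the observed mean. Zero change gives M = 0.704, SD 1.89, t = 2.63, p = 0.006.

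**CNC, assumed mean 20 and SD 20.** The worst fill is about -25, and all six at worst gives t = 4.3, so the grid never loses significance. A common fill loses it at about -66: M = (880 - 397.5)/50 = 9.65; SD² = (17200 + 5.28 × 86.3²)/49 = 1153; t = 9.65/(34.0/7.071) = 2.01. A child can fall by 66 points only from a baseline of at least 66%, so a search might reach the scale limit first. That would be a useful result, and the planned grid cannot show it.

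**The case against.** Several stronger readings are tempting, and the documents do not support them.

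- A reader might infer that the plan tests only the two extremes and says nothing about milder departures. It requires every combination, which gives seven graded scenarios with six missing, and it does locate a tipping count.
- A reader might infer that the CNC conclusion is at risk. At a mean near 79 it is not: even the scale limit for all six leaves t = 6.6. The 79.1 also comes from PBK words in 14 children aged 10 to 17 without single-sided deafness, so it only illustrates.
- A reader might infer that the rule is never as harsh as no benefit. At the documented SSQ gain of 2.10, the all-worst fill is about -2.4 (SD 2) or -4.6 (SD 3), harsher than zero change, and the test still passes (t about 4.6 and 2.6). The SSQ mean of 0.8 used above is an assumption.

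Six missing may also be too many: the adult figure is at 12 months, these endpoints are at 4 weeks or 6 months, and the SAP expects little missing data. With fewer missing, the issue shrinks. In the same SSQ example with two missing (worst -3.74), M = (38.4 - 7.48)/50 = 0.618, SD² = (47 × 4 + 1.92 × 4.54²)/49 = 4.64 and t = 2.03, so the grid never loses significance.

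Finally, these are secondary endpoints; the primary is descriptive safety.

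What survives is the missing size of departure, the missing zero-change scenario and the restriction to the observed range. The mixtures do not repair these, because they confound a worse average with a larger variance.

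**Conclusion.** The concern holds in this limited form. The analysis is mislabelled and does not answer the question its name implies. For a large CNC effect the cost is a misleading description of robustness (worst fill about +35 to +13 points for SD 20 to 30) with no change in conclusion. For modest effects it can mislead in either direction: it can signal fragility at an average fill of -0.7 when a common fill would need about -1.2, or stop at -25 when the tipping value is about -66. All of these sizes rest on assumed SDs, six missing of 50 and roughly normal changes; the SSQ mean of 0.8 and the CNC mean of 20 are also assumed. The main multiple-imputation analysis is unaffected. The amendment is worth making because it is cheap and this is the only planned check on the missing-at-random assumption.

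**What to change.** In SAP 5.6.2.3, 5.6.3.3, 5.6.4.3 and 5.6.5.3:

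1. Relabel the present rule as a best/worst-case enumeration, and say whether observed results means changes or visit scores.
2. Add delta-adjusted multiple imputation. Shift the imputed results of missing children in steps in the clinically adverse direction: down for SSQ and CNC, up for PTA thresholds and BKB-SIN SNR-50. Keep each value within the range possible for that child. Stop when the one-sided p-value exceeds 0.025 or the scale limit is reached, and report that shift.
3. Include a fixed scenario with zero change from baseline for every missing child.
4. Define the sign of the change to match. SAP 5.6.3.1 and 5.6.5.1 take the post-operative minus the pre-operative value and call a positive result improvement, although lower PTA thresholds and lower SNR-50 are better. An instruction simply to lower the imputed values would therefore run the wrong way for those two endpoints.

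The cost is SAP wording and a short extra program, with no change to data collection. The downside is that reported robustness may look slightly less favourable.

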#### 5.6.3 Secondary Endpoint 2 – PTA

Secondary endpoint 2 is defined as the mean difference in individual subject PTA 500, 1, 2, and 4kHz Baseline to 4 Weeks post-surgery.

### 5.6.3.1 Primary Analysis of Secondary Endpoint 2

The secondary endpoint 2 will be assessed with the following hypothesis:

 $H_0$ :  $\Delta \leq 0$ 

 $H_a$ :  $\Delta > 0$ 

where  $\Delta$  represents difference between baseline PTA and 4 Weeks-post surgery PTA, specifically  $\Delta$  =  $PTA_{4 \ Weeks}$  –  $PTA_{preop}$ . This difference is parameterized so that a positive value is indicative of a clinical improvement.

The hypothesis will be evaluated using a one-sample, one-sided 0.025 alpha level t-test for a mean against the null of zero. The objective will be met if the null hypothesis is successfully rejected.

The endpoint will be presented with descriptive statistics and the corresponding two-sided 95% confidence interval based on the t-distribution.

#### 5.6.3.2 Handling of Missing Data

Little missing data is expected for this endpoint. If there is missing endpoint data, a multiple imputation approach will be used based on a fully conditional specification. The imputation model will include the following covariates: age, sex, and baseline PTA. An augmented likelihood approach will be used if need to facilitate modeling. A total of 100 imputed data sets will be generated and results combined for inferential purposes.

Statistical Analysis Plan		Page 10 of 13	
Sponsor	Study		Version
Cochlear Americas	A pivotal, prospective, multi-center, open- label study evaluating the safety and effectiveness of the Cochlear ™ Osia ® 2 System in a pediatric population		1.0

#### 5.6.3.3 Sensitivity Analysis

In the event there is significant evidence of a departure from normality based on a Shapiro-Wilk test at the 0.05 alpha level, a Sign test (a non-parametric alternative) will be employed.

A tipping point analysis for missing data will be performed as a sensitivity analysis. This will impute values for the missing endpoint data, using all possible combinations of the "best" and "worst" observed results for the endpoint (i.e. all missing imputed as "worst", all missing imputed as "best", and all combinations between these extremes).

#### 5.6.4 Secondary Endpoint 3 – CNC Words

Secondary endpoint 3 is defined as the mean difference between baseline unaided speech perception in quiet and the aided condition using the Osia 2 system at 6 months post-surgery on open-set monosyllabic word recognition (CNC Words) in quiet.

### 5.6.4.1 Primary Analysis of Secondary Endpoint 3

The secondary endpoint 3 will be assessed with the following hypothesis:

 $H_0$ :  $\Delta \leq 0$ 

 $H_a$ :  $\Delta > 0$ 

where  $\Delta$  represents difference between baseline unaided speech perception CNC and 6 months-post surgery CNC, specifically  $\Delta$  =  $CNC_{6\,Months}$  –  $CNC_{preop}$ . This difference is parameterized so that a positive value is indicative of a clinical improvement.

The hypothesis will be evaluated using a one-sample, one-sided 0.025 alpha level t-test for a mean against the null of zero. The objective will be met if the null hypothesis is successfully rejected.

The endpoint will be presented with descriptive statistics and the corresponding two-sided 95% confidence interval based on the t-distribution.

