Lau et. al. 2020 reported on the surgical and audiological outcomes using the Osia System in the first 10 United Kingdom patients. Five females and five males participated with a mean age of 52 years (range 30 – 78) who presented with either mixed (n = 5) or conductive hearing losses (n = 3) or single sided deafness (n = 2). All subjects had prior hearing aid experience and were fit with a Baha 5 Power for aided testing prior to implantation with the Osia system. Audiometrically, there was no alteration of the bone conduction thresholds post implantation. Additionally, when the subjects were segmented into the three different audiological indications, the mean gain was + 86.5 dB (range 79–94, SD = 10.6) for single-sided deafness, + 31 dB (range 12–48, SD = 17.3) for mixed and + 22 dB (range 12–31, SD = 9.5) for conductive. The mean functional gain improvement for the study population was +39.4 dB. The authors state that the enhancement in gain appeared to be one of the largest gains amongst bone conduction devices especially in the higher frequencies. Speech recognition as measured by SRT went from 38.1 dB to 22.7 dB at 4 months post-surgery. In addition to objective assessments of outcome, patient-reported outcomes measured by use of the Client Oriented Satisfaction Inventory (COSI) indicated that being able to hear well in real-life situations as well as a decrease in hearing aid disability were significant findings.

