## 8.4 Sample Size Determination

Sample size for the study is not driven by power requirements for a formal statistical hypothesis test. The planned sample size of 50 subjects will provide data to characterize safety and effectiveness with a reasonable degree of statistical precision. Additionally, the planned sample size will allow for a high probability of observing events of interest. For example, with 50 subjects, the half-width of a two-sided 95% confidence interval for a continuous endpoint based on a t-distribution would be 0.284 units on the effect size scale. Similarly, with 50 subjects, there is a greater than 95% probability of observing one or more events that occur at a population rate of 5.9%.

Stratification of the 50 subjects will include a minimum of 10 subjects with single-sided-deafness. In addition, at least one-third (15) of the subjects represented at the youngest ages (5-6 years) will be implanted with the remaining 35 subjects represented by the other age groups as evenly as possible.

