### 5.6.4.2 Handling of Missing Data

Little missing data is expected for this endpoint. If there is missing endpoint data, a multiple imputation approach will be used based on a fully conditional specification. The imputation model will include the following covariates: age, sex, and baseline CNC. An augmented likelihood approach will be used if need to facilitate modeling. A total of 100 imputed data sets will be generated and results combined for inferential purposes.

Statistical Analysis Plan		Page 11 of 13	
Sponsor	Study		Version
Cochlear Americas	A pivotal, prospective, multi-center, open- label study evaluating the safety and effectiveness of the Cochlear ™ Osia ® 2 System in a pediatric population		1.0

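### The imputation models for SSQ, CNC and BKB-SIN leave out hearing-loss type, although the protocol recruits to a minimum number of children with single-sided deafness

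*SAP*

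**What the plan says.** - **Recruitment.** Protocol 8.4 (and 6.2.3): "Stratification of the 50 subjects will include a minimum of 10 subjects with single-sided-deafness". This is a floor in a one-group study without randomisation. Protocol 6.2.1 gives single-sided deafness its own audiometric criterion, separate from conductive or mixed loss. SAP 4 does not repeat the floor.
- **Test.** SAP 5.6.2.1, 5.6.4.1 and 5.6.5.1 use the same unadjusted test: "The hypothesis will be evaluated using a one-sample, one-sided 0.025 alpha level t-test for a mean against the null of zero".
- **Imputation.** Missing endpoint values are multiply imputed by fully conditional specification, with 100 data sets. For CNC (SAP 5.6.4.2): "The imputation model will include the following covariates: age, sex, and baseline CNC". For SSQ (SAP 5.6.2.2): "The imputation model will include the following covariates: age, sex, and baseline SSQ". SAP 5.6.5.2 has the same list with baseline BKB-SIN. Each section expects little missing data and gives no rate.
- **Related provisions.** SAP 5.6.2.3, 5.6.4.3 and 5.6.5.3 plan a tipping-point analysis with best and worst observed values. SAP 5.9 plans subgroups that include etiology of hearing loss, which is not defined as single-sided deafness versus conductive/mixed.
- **Data available.** Screening (Protocol 6.3.1.2 and 6.3.4.1) already documents which type of loss each child has.

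**The concern.** The sponsor considers single-sided deafness important enough to control how many such children are enrolled, yet the models that supply missing outcomes cannot see it. Leaving a variable out of an imputation model assumes that it carries no information about the outcome beyond the covariates that are kept. Here, a missing child with single-sided deafness is predicted from a regression fitted to all observed children, most of whom may have conductive or mixed loss.

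That does harm only when two things hold together: the types differ in mean change, and missingness differs by type. The pooled mean for SSQ, CNC or BKB-SIN is then pulled towards the type with fewer missing values. The direction is not known in advance. If children with single-sided deafness improve less and are missing more often, the benefit is overstated; if they improve more, it is understated. This affects the main estimate and its test, not a side analysis.

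**Working it through.** **Inputs from the documents.** N = 50; at least 10 with single-sided deafness; imputation on age, sex and own baseline; two-sided 95% t interval.

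**Assumed, because the documents do not give them.** The difference in mean change between single-sided deafness and conductive/mixed loss, d, in within-type SDs (1 to 2, with 0 to 2 for context); the number and type of missing children; how far baseline separates the types. The split is taken as 10 and 40.

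**1. The plan's own precision figure.** t(0.975, 49)/√50 = 2.0096/7.0711 = 0.284, as SAP 4 states.

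**2. Shift when only children with single-sided deafness are missing and baseline, age and sex do not predict type.** With m of 10 missing, the expected imputed change is the mean of the 50 − m observed children. That lies 40/(50 − m) × d away from the single-sided-deafness mean. Over 50 children the shift has size (m/50) × 40/(50 − m) × d.

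| m missing | d = 1 | d = 2 |
|---|---|---|
| 2 | 0.04 × 40/48 = 0.033 | 0.067 |
| 3 | 0.06 × 40/47 = 0.051 | 0.102 |
| 5 | 0.10 × 40/45 = 0.089 | 0.178 |

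**3. Scale.** The planned t-test puts the between-type spread into its error term. Its expected variance is 1 + [10 × 40/(50 × 49)] × d² = 1 + 0.1633 d².
- d = 1: SE = √(1.1633/50) = 0.153. Three missing: 0.051/0.153 = 0.33.
- d = 2: SE = √(1.6531/50) = 0.182. Three missing: 0.102/0.182 = 0.56.

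Against the stated half-width of 0.284, two missing children shift the mean by 12% (d = 1) to 23% (d = 2) of that width.

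**4. When the shift disappears.** With d = 0 it is zero. With proportional missingness, say 1 with single-sided deafness and 4 others, the observed share is 9/45 = 0.2 and the shift is (4 × 0.2d − 1 × 0.8d)/50 = 0.

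**5. When baseline carries some of the type.** Simulation (4,000 runs per setting), 2 children with single-sided deafness missing, imputing from age, sex and baseline:

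| Baseline gap between types (SD) | Shift, d = 1 | Shift, d = 2 |
|---|---|---|
| 0 | 0.0333 | 0.0668 |
| 1 | 0.0292 | 0.0579 |
| 2 | 0.0214 | 0.0421 |
| 3 | 0.0146 | 0.0285 |

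A separated baseline reduces the shift but does not remove it.

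**6. The planned t interval and test.** Simulation, 40,000 runs, unit within-type SD. The alternative is an interval with a stratified error term centred at the enrolled shares.

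| Count with single-sided deafness | d | Planned coverage | Stratified coverage | Planned one-sided type I error |
|---|---|---|---|---|
| Fixed at 10 | 0.5 | 95.3% | 94.9% | 0.024 |
| Fixed at 10 | 1 | 96.5% | 95.1% | 0.017 |
| Fixed at 10 | 2 | 98.9% | 95.1% | 0.006 |
| Random, 20% | 0.5 | 95.0% | 94.6% | 0.024 |
| Random, 20% | 1 | 95.0% | 93.3% | 0.023 |
| Random, 20% | 2 | 95.0% | 88.0% | 0.020 |

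With the count fixed, the planned interval is wider than the stratified one by 2.0%, 7.8% and 28.5% at d = 0.5, 1 and 2.

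**The case against.** **The bias needs an unfavourable pattern.** It requires missing values concentrated in one type, while the SAP expects few and plans a tipping-point analysis. This stands as a limit on size. It does not replace the fix: the tipping-point analysis is a sensitivity check that leaves the main imputed estimate as it is, and the etiology subgroup does not enter the imputation.

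**Baseline may already separate the types.** Baseline SSQ reflects everyday listening (Protocol 6.3.4.2), and a child with single-sided deafness has one normal-hearing ear, so some separation on SSQ is plausible. For CNC and BKB-SIN the other ear is plugged or muffed, and the documents do not show whether unaided scores differ by type. Partial separation shrinks the shift.

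Three stronger readings are tempting, and the documents do not support them.

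- **That the planned intervals are too wide and the t-test should be replaced.** The protocol sets a minimum, not a fixed count. With a random share the planned interval has its nominal coverage and the stratified one falls short. Whether the floor fixes the count depends on the natural share of single-sided deafness, which is not given: the chance that 50 unrestricted recruits include fewer than 10 is 98% at a 10% share, 79% at 15% and 44% at 20%. Even at a fixed count the test only errs on the safe side, and the SAP says "Sample size for the study is not driven by power requirements for a formal statistical hypothesis test". A stratified error term targets the mean at the enrolled mix; that is a choice of estimand, not the repair of an error.
- **That missing children are imputed from the wrong group.** The SAP uses one model over all children, conditional on age, sex and baseline. The accurate statement is that the model ignores type.
- **That the cited UK series shows how large the difference is.** It reports gains of 86.5, 31 and 22 dB "when the subjects were segmented into the three different audiological indications", but in ten adults, two with single-sided deafness, on functional gain. It makes a difference by type plausible and gives no size for SSQ, CNC or BKB-SIN in children.

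**Conclusion.** The point holds for imputation. A named recruitment factor, recorded for every child, is missing from the three models, and the main estimate is exposed to bias if missingness differs by type. The size is modest: 0.033 to 0.067 SD with 2 of 10 children with single-sided deafness missing, and 0.051 to 0.102 SD with 3 of 10, the latter about a third to just over half of the planned standard error. These figures rest on an assumed difference of 1 to 2 within-type SDs, a 10/40 split, no missing data in the other type and an uninformative baseline. Relaxing the last two towards proportional missingness or a separated baseline reduces the shift, and without a difference between types there is none.

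It does not extend to the test. The one-sample t-test is defensible as the main analysis, and its 95% interval cannot be called wrong on what the documents say.

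**What to change.** In SAP 5.6.2.2, 5.6.4.2 and 5.6.5.2, add hearing-loss type (single-sided deafness versus conductive/mixed) to the imputation covariates. Leave the one-sample t-test in 5.6.2.1, 5.6.4.1 and 5.6.5.1 as the main test, and do not require a stratified error term.

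The cost is SAP wording and one more parameter in each imputation model. No new data are needed. With complete data the result is unchanged.
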